6.5 Long Term Follow Up After 6 Months

After the 6 month visit, subjects must be evaluated at the Clinical Center (12 months (+/- 2 month) and then yearly (+/- 2 month) thereafter for 5 years and have blood work done as detailed below. Subjects will be seen by their home physician as clinically indicated and the Clinical Center and home physician will continue to communicate.

- Physical examination
- Complete blood counts with differential (annually +/- 1 month)
- Acute care, mineral, hepatic and other panel(annually +/- 1 month)
- Reticulocyte counts (annually +/- 1 month)
- DAT (direct antibody titer) (annually +/- 1 month)
- Flow cytometry of the peripheral blood for GPI-cells (annually +/- 1 month)
- EBV and CMV PCR in the blood (at 12 months only +/- 1 month)
- Thyroid function tests (annually +/- 1 month)
- Bone marrow biopsy and aspiration with cytogenetics (at 12 months +/- 1 month and annually thereafter, as clinically indicated)
- Type and screen (annually +/- 1 month or if clinically indicated)
- Lymphocyte phenotyping (12 months (+/- 1 month) and as clinical indicated)
- If cyclosporine (CsA) is added: CsA levels will be monitored every week (+/- 3 days) for the first month and then every other week (+/- 3 days) for the remainder of the treatment period. Less frequent monitoring may occur if CsA drug level is therapeutic and steady. Dosing will be adjusted to maintain blood level of 200 – 400 ng/ml. More frequent drug serum levels may be obtained as needed to achieve constant therapeutic levels

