6.4 Post Treatment Monitoring 4 Months to 6 Months

After the 3 month visit, subjects will be followed by their home physician or at the Clinical Center and have blood work done as detailed below. Progress notes and laboratory results from home physicians will be faxed to the Research nurse, [name], [contact]. Subjects must be evaluated at the Clinical Center at the 6 month (\pm 7 days) time point

- Physical examination
- Complete blood counts with differential (every other week +/- 3 days)
- DAT (direct antiglobulin test) (6 months +/- 1 month)
- Type and screen (at 6 months only +/- 2 weeks)
- Acute care, mineral, hepatic and other panel (every other week +/- 3 days) (Home MDs: electrolytes, transaminases, urea nitrogen (BUN), serum creatinine, total bilirubin)
- EBV and CMV PCR in the blood monthly (+/- 2 weeks) to 6 months.
- Reticulocyte count (at 6 months only, Home MDs only if available)
- Thyroid function tests (at 6 months only +/- 1 month)

- Bone marrow biopsy and aspiration with cytogenetics (6 months (+/- 1 month only)
- Flow cytometry of the peripheral blood for GPI-cells (6 months (+/- 1 month only)
- If Cyclosporine (CsA) is added: CsA levels will be monitored every week (+/- 3 days) for the first month and then every other week (+/- 3 days) for the remainder of the treatment period. Less frequent monitoring may occur if CsA drug level is therapeutic and steady. Dosing will be adjusted to maintain blood level of 200 – 400 ng/ml. More frequent drug serum levels may be obtained as needed to achieve constant therapeutic levels.

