8.2 Secondary Endpoints

8.2.1 Transfusion-independence for red blood cells and/or platelets: ability to maintain a hemoglobin >8gm/dl and a platelet count > 20 000/ μ L without the need for transfusions for a period of 6 weeks regardless of subsequent events.

8.2.2 Overall survival which is defined as the time elapsed between time of treatment and death and will be compared between responders and non-responders. Any such comparison may be biased and needs to be interpreted cautiously.

8.2.3 Life threatening toxicity. Subjects who do not complete the treatment course because of toxicity or voluntary withdrawal will be included in analyses.

8.2.4 Overall survival and transformation-free survival, which is defined as the time elapsed (reported at 3 month intervals for the first four years, then yearly thereafter) between time of treatment, and bone marrow morphologic evidence for progression (as determined by FAB criteria), development of acute leukemia, or death will be compared between responders and non-responders. Any such comparison may be biased and needs to be interpreted cautiously.

8.2.5 Response duration will be determined as the interval between time of onset of response as outlined above, and the time of relapse or loss of response characteristic (reported at 3 month intervals for the first four years, then yearly thereafter).

8.2.6 Affects of the addition of cyclosporine. Subjects who relapse after responding to Campath will be given CsA to determine if CsA will be beneficial under these circumstances. For this protocol, CsA is investigational, subjects will be followed, data will be collected and analyzed as secondary endpoints. The number of subjects who will receive CsA cannot be predicted since it will depend on the initial response to Campath which is unknown.

Response proportion, response duration, overall survival, and transformation free survival will be determined and compared within the FAB sub-groups and International Prognostic Scoring System categories of MDS and with the results of previous studies at the NIH using h-ATG alone or CsA alone to treat the cytopenia of MDS.

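### Response duration and transformation-free survival are to be reported every 3 months for four years, but after month 6 the scheduled assessments are about yearly, so relapses dated at detection will tend to overstate response duration

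*Combined protocol and SAP*

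**What the plan says.** **Reporting.** Section 8.2.5 measures response duration from onset of response to "the time of relapse or loss of response characteristic (reported at 3 month intervals for the first four years, then yearly thereafter". For transformation-free survival, section 8.2.4 uses the same grid: "which is defined as the time elapsed (reported at 3 month intervals for the first four years, then yearly thereafter) between time of treatment". The clock stops at the first of "bone marrow morphologic evidence for progression (as determined by FAB criteria), development of acute leukemia, or death".

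**Assessment.** In months 4 to 6, section 6.4 has "Complete blood counts with differential (every other week +/- 3 days". After month 6, section 6.5 places Clinical Center visits at "12 months (+/- 2 month) and then yearly (+/- 2 month) thereafter for 5 years", with counts on the annual schedule, "Complete blood counts with differential (annually +/- 1 month". For marrow it has "Bone marrow biopsy and aspiration with cytogenetics (at 12 months +/- 1 month and annually thereafter, as clinically indicated".

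**Between visits.** Section 6.5 says "Subjects will be seen by their home physician as clinically indicated and the Clinical Center and home physician will continue to communicate". It gives no frequency for home counts. Sections 6.3 and 6.4 require home physicians' notes and laboratory results to be faxed to the study; section 6.5 has no such requirement.

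**Relapse.** Appendix B defines loss of response mainly by counts (a fall in granulocytes, platelets or hemoglobin) or by transfusion dependence.

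**Analysis.** Section 8.4 names Kaplan-Meier, Cox, cumulative incidence and competing-risk methods, and mentions random censoring. It names no interval-censored method and no rule for dating a relapse.

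**The concern.** A 3-month grid implies that each relapse can be placed within about 3 months. After month 6 the schedule places it only within the gap between two counts, which is 6 months at first and then 12. Such times are interval-censored: the relapse lies between the last count in response and the first without it.

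The usual default is to enter the detection date as the event date and run Kaplan-Meier. That can only move recorded relapses later, so response duration comes out too long and the quarterly figures look more precise than they are.

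Section 8.2 compares response duration across FAB subgroups and IPSS categories and with previous NIH studies of h-ATG alone or CsA alone. A difference in how often patients were assessed could then be read as a difference in durability.

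**Working it through.** **Plan's own figure.** The plan states no sample size, power or precision for either endpoint. Its one derivable figure, the two-stage design of section 8.3 (6/19, then 16/39), reproduces exactly: type I error 0.0455, power 0.8036. It rests on the 3-month response and does not depend on section 6.5.

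**Step 1: grid against schedule.** Quarterly points to month 48 are 3, 6, ..., 48, or 16 points. Scheduled counts fall on months 3, 6, 12, 24, 36 and 48, or 6 of 16. After month 6 they fall on 4 of 14. With the ±1 month count window an annual gap can reach 12 + 2 = 14 months; with the ±2 month visit window, 12 + 4 = 16. For marrow, month 12 is the only point after month 6 not qualified by clinical indication.

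**Step 2: delay from dating at detection.** Assumptions, since the documents give none: exponential relapse with median duration m of 6 to 36 months, and follow-up to month 60. With λ = ln 2 / m and a gap of L months between counts, the mean delay for a relapse inside the gap is

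d(L) = L / (1 − e^(−λL)) − 1/λ.

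Example with m = 12: λ = 0.0578 and 1/λ = 17.31.

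- Months 6 to 12: d(6) = 6/0.2929 − 17.31 = 3.17
- Each later year: d(12) = 12/0.5 − 17.31 = 6.69
- Among patients still in response at month 6, the share relapsing in months 6 to 12 is 0.2929. The share relapsing in months 12 to 60 is 0.7071 × (1 − 0.5⁴) = 0.6629.
- Mean delay = (0.2929 × 3.17 + 0.6629 × 6.69) / 0.9558 = 5.61 months

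If a fraction f of relapses is caught promptly between visits, the mean delay is multiplied by (1 − f): 5.61 × 0.5 = 2.81 and 5.61 × 0.2 = 1.12.

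A simulation of 1,000,000 responders per scenario (onset at month 3, counts every 2 weeks to month 6, then months 12, 24, 36, 48 and 60) agrees. Mean delay in months for relapses after month 6:

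| Assumed median | Annual, none caught | Half caught | 80% caught | 3-monthly counts, none caught |
|---|---|---|---|---|
| 6 | 5.34 | 2.67 | 1.07 | 1.59 |
| 12 | 5.61 | 2.81 | 1.13 | 1.54 |
| 18 | 5.67 | 2.84 | 1.14 | 1.53 |
| 24 | 5.69 | 2.85 | 1.14 | 1.52 |
| 36 | 5.69 | 2.84 | 1.14 | 1.51 |

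**Step 3: effect of the dating rule.** Mean response duration restricted to month 60, annual schedule, none caught between visits, in months:

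| Assumed median | True | Detection date | Midpoint | Last count in response |
|---|---|---|---|---|
| 6 | 8.63 | 12.46 | 9.23 | 5.99 |
| 12 | 16.65 | 21.20 | 17.08 | 12.96 |
| 18 | 23.08 | 27.53 | 23.38 | 19.22 |
| 24 | 27.97 | 32.11 | 28.18 | 24.26 |
| 36 | 34.60 | 38.09 | 34.72 | 31.35 |

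Detection dating adds 3.5 to 4.6 months (38.09 − 34.60 = 3.49; 21.20 − 16.65 = 4.55). Midpoint dating adds 0.1 to 0.6. Dating at the last count in response subtracts 2.6 to 3.9. The unstated rule therefore decides both the sign and most of the size.

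**Transformation-free survival.** Steps 2 and 3 do not carry over. Its events are marrow progression, leukemia or death, not count changes, and no bias has been computed for it.

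**The case against.** The best defence is that many relapses will not wait for an annual count. Transfusion dependence is itself a relapse criterion and can be dated between visits. Home physicians see patients when needed and stay in touch with the Clinical Center. Section 5.2.2 adds CsA at relapse, so a relapse brings the patient back to the study. This stands as a limit on size, and the half-caught and 80%-caught columns show how much it matters. It does not remove the point, because section 6.5 requires neither home counts at any interval nor transfer of results.

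Several stronger readings are tempting, and the documents do not support them:

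- *Durations are certain to be overstated.* That needs detection dating, which the plan does not state, and few relapses caught between visits.
- *Section 8.4 prescribes a wrong method.* Its list is open-ended, and the Kaplan-Meier and Cox sentence is written for time to response. The gap is a missing rule for response duration.
- *Medians are inflated by most of a year.* With onset at month 3 and none caught between visits, true medians of 12 and 18 are both recorded as 21, and 24 as 33. The recorded curve has its large steps only at the annual counts. With half caught, 12 becomes 15.7 and 24 becomes 27.3. The mean delay is the steadier measure.
- *Transformation-free survival is distorted by sparse counts.* Only its marrow-defined events are affected, through the marrow schedule. Deaths can be dated exactly.
- *The comparison with earlier NIH studies is biased.* The documents do not give those studies' assessment schedules, so this is possible but not shown.

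**Conclusion.** The mismatch between sections 8.2.4 to 8.2.5 and section 6.5 is plain on the text and needs no assumption. Its effect on response duration is conditional. If relapses are dated at detection and analysed as right-censored, response duration will tend to be overstated. Relapses after month 6 are then dated on average 5.3 to 5.7 months late with none caught between visits, about 2.8 with half caught and about 1.1 with 80% caught. These figures rest on exponential relapse, assumed medians of 6 to 36 months and assumed catch rates.

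Relapses before month 6 are dated to about two weeks, and the first gap is 6 months, not a year. For transformation-free survival the marrow-defined events are interval-censored by the marrow schedule, with no size established. The 3-month primary endpoint, the two-stage design and the safety stopping rule are unaffected. This should be put right before the secondary results are reported, but it does not threaten the main conclusion.

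**What to change.** 1. For each responder, record the date of the last assessment in response and of the first showing relapse, using any home-physician counts or transfusion dates already held. Flag whether each date came from a scheduled or an as-needed assessment: the latter are prompted by symptoms, and standard interval-censored methods assume assessment times unrelated to the event.
2. State the relapse-dating rule in section 8.2.5.
3. Analyse response duration and the non-death events of transformation-free survival with an interval-censored method (the Turnbull estimator or a parametric model), as the main analysis or at least beside Kaplan-Meier. Enter deaths at their exact dates.
4. Report on the scheduled-visit grid (months 6 and 12, then yearly) instead of every 3 months, so that sections 6.5 and 8.2 agree.

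The cost is a few lines of analysis-plan text, standard software and some abstraction from existing records. Confidence intervals will be wider and reported times coarser, which reflects what the visits can show. Adding 3-monthly counts prospectively is not an option: section 10.4 places the study in data analysis only from January 27, 2017. Section 10.6 says data are still being analysed for a manuscript, so the change can still affect what is reported.

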7.0 LABORATORY RESEARCH STUDIES

Intended use: During the course of participating on this study, an additional 105 cc of blood (at baseline) , 5 cc (Day 5), 10 cc (Day 10), or 50 cc of blood (at 1 month post treatment), 45 cc of blood (3months, 6 months and 12 months post treatment), 20 cc of blood (annually thereafter) and 5 cc of bone marrow aspirate (baseline, 6 months, 12 months, and annually thereafter as clinically indicated) may be collected for exploratory ancillary laboratory research studies which have been approved by the IRB and are listed in Appendix A. These studies will not be used to assess the primary endpoint, may or may not be done, and if done, may be correlated with the presence or absence of response. These specimens will not be read by a pathologist or used for diagnostic purposes. Campath research studies may include:

- Anti-alemtuzumab (Campath®) antibody may be measured.
- Drug sensitivity testing assessment may be collected. In order to assess the mechanisms of infusion related toxicities (fever, hypotension, wheezing, rash, etc.) following alemtuzumab (Campath®). Blood sample will be collected at baseline and 2-4 hours after alemtuzumab (Campath®) infusion and correlated with clinical adverse events:

- Tryptase (2.5 ml blood)
- Inflammatory cytokines (e.g., TNF-a, IL-1ra, IL-6) and IL-10

Storage: Research samples will be stored with identifiers (subject initials, data time point, and date of sample collection) in the secure laboratory of the principal investigator.

Tracking: Samples will be ordered and tracked through the CRIS Research Screens. Should a CRIS screen not be available, the NIH form 2803-1 will be completed and will accompany the specimen and be filed in the medical record. Specimens will be entered in the NHLBI Biospecimen Inventory System (BSI). Samples will not be sent outside NIH without IRB notification and an executed MTA.

End of study procedures: Samples from consenting subjects will be stored until they are no longer of scientific value or if a subject withdraws consent for their continued use, at which time they will be destroyed.

Loss or destruction of samples: Should we become aware that a major breach in our plan for tracking and storage of samples has occurred, the IRB will be notified.

8.0 BIOSTATISTICAL CONSIDERATIONS

8.1 Primary Endpoint

The primary endpoint is hematologic response measured at 3 months after first dose alemtuzumab (Campath®) sustained on at least two serial measurements at least one week apart at landmark time points (3, 6 and 12 months) will be defined using standard hematologic and cytogenetic response criteria for MDS (See Appendix B for detailed description)⁷⁷.

Complete response: Normalization of all affected cell lines (Hemoglobin, Reticulocyte count, Platelets, ANC)

Partial response: At least one minor response

1. Hemoglobin Response

Major response: For subjects with pretreatment hemoglobin less than 11 g/dL, greater than 2 g/dL increase in hemoglobin; for RBC transfusion-dependent subjects, transfusion independence or an absolute reticulocyte count to $\geq 60,000/\mu\text{L}$ of blood in transfusion-dependent patients.

Minor response: For subjects with pretreatment hemoglobin less than 11 g/dL, 1 to 2 g/dL increase in hemoglobin; for RBC transfusion-dependent patients, 50% decrease in transfusion requirements.

2. Platelet response

Major response: For subjects with a pretreatment platelet count less than $100,000/\text{mm}^3$, an absolute increase of $30,000/\text{mm}^3$ or more; for platelet transfusion-dependent subjects, stabilization of platelet counts and platelet transfusion independence.

Minor response: For subjects with a pretreatment platelet count less than 100,000/mm³, a 50% or more increase in platelet count with a net increase greater than 10,000/mm³ but less than 30,000/mm³.

3. ANC response

Major response: For absolute neutrophil count (ANC) less than 1500/mm³ before therapy, at least a 100% increase, or an absolute increase of more than 500/mm³ whichever is greater.

Minor response: For ANC less than 1500/mm³ before therapy, ANC increase of at least 100%, but absolute increase less than 500/mm³.

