8.3 Sample Size

Because the efficacy of this treatment is almost completely unknown, we would like to reject the treatment as quickly as possible with a small number of subjects if the treatment is not effective.

A response probability of 30% or less would warrant terminating the treatment on this subject population, and we hypothesize that the actual response probability using this treatment would reach 50% or more.

Let p be the probability of complete or partial response at 3 months. Our sample size is determined by testing the null hypothesis $H_0: p \leq 30\%$ versus the alternative $H_1: p \geq 50\%$ at 0.05 significance level and 0.80 of the power. We determine the sample size using the Two-Stage Minimax Design outlined in Table 1 of Simon (1989)⁷⁵ This design is selected because it requires a smaller total number of subjects ($n=39$) than the Simon's Two-Stage Optimal Design ($n=46$). At the first stage, 19 subjects will be accrued and the null hypothesis will be accepted (i.e., the treatment will be terminated) if 6 or less subjects respond to the treatment at 3 months. If 7 or more subjects respond to the treatment at 3 months in the first stage, then an additional 20 subjects will be accrued, bringing the total number of subjects to $n=39$. The null hypothesis of $p \leq 30\%$ will be accepted if the total number of complete and partial responders at 3 months is 16 or less.

An additional 39 subjects will be enrolled to allow for statistically valid subgroup comparisons of secondary endpoints such as response to cyclosporine in subjects who relapse within six months of treatment.

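### Read literally, the partial-response definition in section 8.1 leaves out subjects whose only responses are major, count-based gains short of normal

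*Combined protocol and SAP*

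**What the plan says.** Section 8.1 sets the endpoint: "The primary endpoint is hematologic response measured at 3 months after first dose alemtuzumab". It then gives two overall categories. The first is "Complete response: Normalization of all affected cell lines". The second is "Partial response: At least one minor response". Major and minor grades follow for hemoglobin, platelets and ANC. For hemoglobin counts, major is "greater than 2 g/dL increase in hemoglobin" and minor is "1 to 2 g/dL increase in hemoglobin". For platelets, major starts at a gain of 30,000/mm³, and minor needs a rise of at least 50% with a net gain above 10,000 but below 30,000. For ANC, minor needs at least a doubling with a gain below 500/mm³. For red-cell transfusion-dependent subjects, major is transfusion independence or a reticulocyte threshold, and minor is a 50% decrease in requirement.

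Section 8.3 takes only the two overall categories into the test: "Let p be the probability of complete or partial response at 3 months". The rule is to stop if 6 or fewer of 19 respond, and to accept the null if 16 or fewer of 39 respond.

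**The concern.** The major grade is defined for each cell line, but the overall response definition never uses it. Because the count-based minor bands have upper limits, a gain above the limit leaves the minor band without entering any category that 8.3 counts, unless every affected line has also normalised. A larger improvement can then score as non-response while a smaller one scores as partial response.

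This matters because the label is the primary endpoint. It decides the look at 19 subjects and the final decision at 39. It also defines the responder groups for the survival and response-duration comparisons in section 8.2. Two assessors could score the same record differently, and at 6 versus 7 responders of 19 a single record changes the decision.

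**Working it through.** **1. The bands compared**

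| Line | Minor | Major | Can a major response also be minor in that line? |
|---|---|---|---|
| Hemoglobin (count) | +1 to 2 g/dL | more than +2 g/dL | No |
| Platelets (count) | at least +50%, net gain above 10,000 and below 30,000/mm³ | +30,000/mm³ or more | No |
| ANC | at least +100%, gain below 500/mm³ | +100% or more than +500/mm³, the greater applying | No, if the larger threshold must be met; if either is enough, a doubling of less than 500 is both |
| Red-cell transfusion | 50% decrease, no upper limit stated | independence, or reticulocytes at least 60,000/µL | Possibly: independence is a 100% decrease |

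**2. Two records scored as written, platelets the only affected line**

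- 20,000 to 35,000/mm³: gain 15,000, which is 15,000/20,000 = 75%. Minor, so a partial response.
- 20,000 to 60,000/mm³: gain 40,000. Major. Not minor, because the gain is not below 30,000. Not normal, taking the complete-remission threshold of 100,000/mm³ in Appendix B. Neither complete nor partial response.

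Hemoglobin behaves the same way when it is the only affected line and is judged on counts: 7.0 to 8.5 g/dL (+1.5) is a partial response, while 7.0 to 10.0 g/dL (+3.0) is neither, since Appendix B asks for more than 11 g/dL.

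**3. Whether Appendix B closes the gap**

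It does not. Its partial remission requires the complete-remission blood values plus a marrow change, which is a different concept from 8.1's partial response. Its part III grades hematologic improvement as major or minor but maps neither grade to partial response.

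**4. The plan's own design figure**

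Inputs from 8.3: null rate 0.30, alternative 0.50, stage 1 limit 6 of 19, final limit 16 of 39. With b(x; n, p) the binomial probability:

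- P(reject) = Σ over x = 7 to 19 of b(x; 19, p) × P[Bin(20, p) ≥ 17 − x]
- P(stop at stage 1) = P[Bin(19, p) ≤ 6]

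At p = 0.30, P(reject) = 0.0455. At p = 0.50, P(reject) = 0.804. An exhaustive search confirms 6/19, 16/39 as the minimax design for 0.05 and 0.80. The stated n = 39 is reproduced.

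**5. Sensitivity to literal scoring**

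Assume that the 50% in 8.3 is the true rate of any response (complete, major or minor). Let f be the share of those responders whose only responses are major, count-based and not normalised. The documents do not give f. The scored rate is 0.50 × (1 − f).

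| f (assumed) | Scored rate | Power | P(stop at stage 1) |
|---|---|---|---|
| 0 | 0.500 | 0.804 | 0.084 |
| 5% | 0.475 | 0.710 | 0.12 |
| 10% | 0.450 | 0.599 | 0.17 |
| 20% | 0.400 | 0.356 | 0.31 |

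Literal scoring can only remove responders, so it does not inflate the false-positive rate. The error runs against the treatment.

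**The case against.** The strongest reply is that the definition sets a floor, meaning minor or better. That is probably what the authors meant. Section 2.4.1 reports earlier results as transfusion independence, which 8.1 grades as major; section 10.4 counts abolition of transfusion need as a benefit; and nothing in the documents calls a major responder a non-responder. This stands as a statement of intent. It does not settle the text: the wording puts its minimum on the number of responses rather than their grade, and the capped bands sit badly with a floor.

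Four stronger readings are tempting, and the documents do not support them:

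- *Every major response is excluded from minor.* This fails for red-cell transfusion-dependent subjects. The 50% decrease has no upper limit, so independence can be read as meeting it. It therefore cannot be said that independence scores as failure while halving scores as success. This limb is not marginal, since transfusion-dependent anemia is the first entry route in 4.1.2.
- *Every major responder short of normal is lost.* A minor response in any other line still makes the subject a partial responder. Section 4.1.1 admits RCMD and RCMD-RS, which Table 3 describes with two or three cytopenias, so this will apply to some subjects.
- *Such subjects would be taken off study.* Sections 5.2.1 and 8.6 refer to failure to respond without tying it to the categories in 8.1, and 8.6 lists it under investigator decision.
- *The power figures forecast a loss.* They depend on an assumed f and on analysts applying a reading that was probably not intended.

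Timing also limits the effect. Section 10.4 places the study in data analysis only as of January 27, 2017, so clearer wording cannot alter a stage 1 decision already taken. It still governs the reported responder count.

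**Conclusion.** The point holds for count-based responses. As written, a subject whose only responses are major and not normalised falls outside both categories that the primary test counts, while a smaller gain falls inside. That is certain for hemoglobin and platelets. For ANC the two bands separate cleanly only if the greater threshold is required. For red-cell transfusions the text is ambiguous.

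This is a wording defect in the primary endpoint, not a sample-size error. Its size cannot be fixed from the documents: if no such subjects exist, or if scoring is minor or better, the loss is zero. If the true response rate is 50% and literal scoring loses 5% to 20% of responders, power is 0.71 to 0.36 instead of 0.80. Even a small share is costly, so the rule should be written down before the responder count is reported.

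**What to change.** In section 8.1, replace the definition with: *Partial response: at least one major or minor response in any affected cell line, not meeting complete response.* State the minor red-cell transfusion limb as *at least a 50% decrease*. Apply this one rule to every subject in the final responder count, and say in the report that it was applied.

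The sponsor should also reconcile the references to failure to respond in sections 5.2.1 and 8.6 with section 8.1. How that bears on treatment or on leaving the study is for the sponsor; no clinical rule is proposed here.

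The cost is two short edits to 8.1 and a check of existing response records. The sample size and the 6/19 and 16/39 boundaries do not change, and no new data, visits or subjects are needed.
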